6. OTHER ANALYSES

6.1. Immunogenicity Analyses

Immunogenicity analyses will use the PPI and/or NI set (as applicable). Where relevant, immunogenicity analyses will include SARS-CoV-2 serostatus at baseline as a subgroup. Immunogenicity analyses will also be done on the FAS (participants who became infected during

the study will be analyzed as a subgroup and shown in the graphs using different colors and symbols). Data will be analyzed by vaccine group.

Key immunogenicity assay results will also be analyzed for the subgroups defined in Section 5.2.1.

Data will be presented by scheduled time point. For the PPI analysis, samples taken outside of the allowed window as described in section 5.1.3 will be excluded from the tables and graphs (but will be included in the listings and clearly marked as results not included in the PPI analyses). For the FAS analysis, samples taken outside of the allowed window will be included.

Note: analyses that are potentially unblinding at the individual participant level (e.g. graphs showing individual data tied to COVID-19 infection status, especially when the number of COVID-19 infections is low and/or when time of infection is indicated) will be carried out after official unblinding of the trial, or will be carried out exclusively on specific groups (or other clearly defined subgroups) after these are unblinded. Alternatively, prior to unblinding, these analyses can be performed in a completely blinded manner (e.g. tables with only a single column pooling all regimens).

The following exploratory analysis will be performed on the sub-study for descriptive purposes:

- Transcriptomics: The relative quantity of transcripts (as measured by mRNA sequencing) in whole blood following vaccination will be measured. The magnitude and type of differentially expressed genes relative to baseline and their kinetics will be compared post dose 1 and post dose 2, and between dose levels. Details are described in separate a study plan and Omics Statistical Analysis Plan.
- Proteomics: The relative abundance of serum proteins following the first and second dose of different Ad26.COV2.S dose levels will be measured relative to baseline and compared between dose levels. Details are described in a separate study plan and Omics Statistical Analysis Plan.
- Circulating spike: The concentration of circulating Spike protein over time in participants who received selected Ad26.COV2.S dose levels will be measured and compared between doses. Details will be described in a separate study plan.

6.1.1. Parameters

The following humoral immune responses may be measured. However, not all assays might be available for all immunogenicity analyses covered by this SAP. Further information on which assays will be analyzed in each of the analyses, will be included in the corresponding DPS documents.

Table 7: Summary of Humoral Immunogenicity Assays

Assay	Purpose
Humoral Immunogenicity	
Primary/Secondary/Exploratory endpoints	
SARS-CoV-2 binding antibodies (ELISA)	Analysis of antibodies binding to SARS-CoV-2 or individual SARS-CoV-2 proteins (eg, S protein)
Exploratory endpoints	
SARS-CoV-2 neutralization (VNA)	Analysis of neutralizing antibodies to the wild-type virus and/or pseudovirion expressing S protein, including emerging SARS-CoV-2 variants
SARS-CoV-2 binding antibodies (ELISA or equivalent assay)	Analysis of binding antibodies to SARS-CoV-2 proteins (eg, S-protein), including emerging SARS-CoV-2 variant proteins.
SARS-CoV-2 binding antibodies (non-S-ELISA and/or SARS-CoV-2 immunoglobulin assay)	Analysis of antibodies binding to the SARS-CoV-2 N protein
Adenovirus neutralization	Adenovirus neutralization assay to evaluate neutralizing antibody responses against the Ad26 vector
Functional and molecular antibody characterization	Analysis of antibody characteristics including Fc-mediated viral clearance, avidity, Fc characteristics, Ig subclass and IgG isotype
Epitope-specificity characterization	Analysis of site-specificity, epitope mapping
Cytokine profiling, and analysis of circulating Spike protein	Analysis of cytokines, chemokines, and other proteins of the innate or adaptive immune response in the serum or plasma, and analysis of circulating Spike protein.
Passive transfer	Analysis of immune mediators correlating with protection against experimental SARS-CoV-2 challenge in a suitable animal model

Innate Assessments (Exploratory endpoints)

Gene expression analysis	Analysis of gene expression by RNA transcript profiling in whole blood (ex vivo, PaxGene tubes)
Proteomic and/or lipidomic approaches, and analysis of circulating Spike protein	Analysis of protein translates (including circulating Spike protein) or lipid mediators in serum or plasma.

ELISA = enzyme-linked immunosorbent assay; Fc = crystallizable fragment; Ig = immunoglobulin; SARS-CoV-2 = severe acute respiratory syndrome coronavirus-2; VNA = virus neutralization assay

6.1.2. Handling of Missing and/or Unquantifiable Immune Response Data

1. Missing immune response data will not be imputed.
2. Values below the lower limit of quantification (LLOQ) or limit of detection (LOD) will be handled as follows:
 - Calculation of geomean and median:

- Values < LLOQ are imputed with LLOQ/2

For Ad26 VNA,

- o Values < LOD are imputed with LOD/2
- o Values between LLOQ and LOD are imputed with $(LLOQ + LOD) / 2$
- Calculation of fold increases from baseline:
 - values < LLOQ are imputed with LLOQ

For Ad26 VNA,

- o Values < LOD are imputed with LOD
- o Values between LLOQ and LOD are imputed with $(LLOQ + LOD) / 2$

3. Values above the upper limit of quantification (ULOQ) will be handled as follows:

- Calculation of geomean and median:
 - Values > ULOQ are imputed with ULOQ.
- Calculation of fold increases from baseline:
 - Values > ULOQ are imputed with ULOQ.

If >10% of data points in PPI or NI Set data values are > ULOQ, a selection of descriptive immunogenicity assessments will be repeated without a ULOQ.

6.1.3. Handling of Changes in Assay Status Throughout the Study Conduct

In case of changes in assay status, from “qualified” to “validated”, the LLOQ and ULOQ are likely to change as well. Should this happen, then the SDTM database will contain records pertaining to the assay in the qualified status and records pertaining to the validated status, and the LLOQ and ULOQ values will also differ.

The statistical analysis will use the LLOQ and ULOQ values associated with the validated assay and will retrospectively apply these on all the data pertaining to the assay, including the data obtained while the assay status was “qualified”. This may imply that data received, statistically analyzed, and presented at an earlier time may change. Graphical displays will show the eventually used LLOQ and ULOQ values. Graphs and tables will have an additional footnote, that reflects the assay status.

6.1.4. Humoral Assays

For **S-ELISA** and **VNA** assay (both wild-type virus and pseudo-virion expressing S protein, for the original strain but also on the emerging variants as available), the following results will be calculated: N, geometric mean^{1§} and corresponding 95% CI of the actual values and fold increases from baseline, fold increase from pre-dose 2 (for time points after dose 2) will be tabulated and graphically presented.

This will be applied for both main study analysis and sub study analysis.

For the calculation of the geometric mean and its corresponding 95% CI, the arithmetic mean, and its corresponding 95% CI are calculated on the \log_{10} transformed values. These values are back transformed to provide the geometric mean and its corresponding 95% CI.

For S-ELISA, wild type, and pseudo-virion VNA (including emerging variants) separately:

- A sample will be considered positive if its value is strictly $>$ LLOQ.
- The following responder definition (Janssen responder definition) will be used as the core definition to assess sero-response rates. A post-baseline sample will be considered a responder if at least one of the following conditions is satisfied.
- The baseline (pre-dose 1) sample value is \leq LLOQ and the post-baseline sample is strictly $>$ LLOQ
- The baseline (pre-dose 1) sample value is strictly greater than the LLOQ ($>$ LLOQ) and the post-baseline sample value represents an at least 4-fold (\geq 4-fold) increase from the baseline sample value.

An alternative responder definition (definition requested by FDA for other studies) may be used for exploratory purposes only to assess sero-response rate in addition to the one above. In such cases, separate tables including sero-response rates with this alternative responder definition will be generated. Under the FDA responder definition, a post-baseline sample will be considered a responder if at least one of the following conditions is satisfied:

- The baseline (pre-dose 1) sample value is $<$ LLOQ and the post-baseline sample is \geq 4x LLOQ.
- The baseline sample (pre-dose 1) value is $>$ LLOQ and the post-baseline sample value represents a \geq 4-fold increase from the baseline sample value.

Actual values are tabulated and shown as dot plots with dots for participant values, and the corresponding geometric mean and 95% CI per time point for each assay. In addition, GMC plots over time, combining the regimens in one graph (without individual participant dots) will also be generated.

- Participant profiles of the actual values over time will be graphically presented.
- Reverse distribution curved of the actual values are provided for selected time points.
- In the graphs, original values will be displayed in the \log_{10} scale.

- Further details and/or updated rules or graphs will be provided in the DPS.

The ratio of binding antibodies (S-ELISA) to wild type VNA, and the ratio of binding antibodies (S-ELISA) to pseudo-virion expressing S protein VNA (including emerging variants) will be calculated for each time point. Values < LLOQ will be imputed with LLOQ for the calculation of the ratios.

In addition, the ratio of the fold increase from baseline in binding antibodies (S-ELISA) to the fold increase from baseline in wild type VNA, and the ratio of the fold increase from baseline in binding antibodies (S-ELISA) to the fold increase from baseline in pseudo-virion expressing S protein VNA will be calculated for each post-baseline time point. Values < LLOQ will be imputed with LLOQ for the calculation of the fold increase ratios.

The following statistics will be calculated and tabulated: N, geometric mean and corresponding 95% CI of the ratio. Graphical displays will also be prepared, showing – for each time point – the geometric mean of the ratio and its 95% CI, together with the individual data points (dot plot).

If a similar assay is performed at different analyzing labs, then separate statistical analyses may be performed.

Correlation (at selected timepoints)

The correlation between the binding antibody (ELISA) titers and neutralizing antibody (VNA) titers to SARS-CoV-2 will be assessed in a subset of participants at selected timepoints using spearman's rank correlation. ELISA (S-ELISA; EU/mL) and VNA (wtVNA or psVNA including emerging variants; IC50) titers. This will be applied for both main study analysis and sub study analysis, as available.

Adenovirus 26 neutralization will be measured in a subset of participants at Day 1 and at Day 57 to assess the impact of pre-existing Ad26 neutralizing antibodies in humoral immunogenicity against SARS-CoV-2 (S-ELISA, psVNA including emerging variants and/or wtVNA). Ad26 VNA sample values >LOD are considered positive.

Descriptive statistics (N, geometric mean and corresponding 95% CI, number, and percentage of positive samples) will be calculated. Spearman correlation between Ad26 VNA at Day 1 (if sufficient number of Ad26-seropositive participants) or Day 57 and S-ELISA concentrations or psVNA including emerging variants or wtVNA titers at Day 29 or Day 71, respectively, will be calculated and visualized with a scatterplot.

Scatterplots between humoral assay results will be provided for selected time points. These may include but are not limited to:

Binding antibodies (S-ELISA) versus wild type VNA

Binding antibodies (S-ELISA) versus pseudo-virion expressing S protein VNA (including emerging variants)

Wild type VNA versus pseudo-virion expressing S protein VNA

Ad26 VNA versus binding antibodies (S-ELISA)

Ad26 VNA versus wild-type VNA

Ad26 VNA versus pseudo-virion expressing S protein VNA (including emerging variants)

If a similar assay is performed at different analyzing labs, then the statistical analyses may distinguish between these and provide separate scatterplots for each analyzing lab versus the other assay of interest. These scatterplots will display the values as analyzed for the geometric mean calculations. Spearman's rank correlation coefficients will also be provided (one per scatterplot).

Further details and/or updated rules will be provided in the DPS.

Definition of SARS-CoV-2 infections

A SARS-CoV-2 infection is defined as a participant with:

- serologic conversion between baseline (Day 1; pre-vaccination) and selected timepoints post-vaccination using an ELISA and/or SARS-CoV-2 immunoglobulin assay that is dependent on the SARS-CoV-2 N protein (e.g., N-ELISA or equivalent assay, such as the Roche Elecsys anti-SARS-CoV-2 assay), for participants that are N serology negative at baseline, or
- reported positive SARS-CoV-2 PCR test during the study.

For participants with missing N serology result at baseline, a post baseline positive N serology result will not be considered a COVID-19 infection.

Assessment of occurrence of asymptomatic SARS-CoV-2 infection

Serologic conversion between baseline (Day 1; pre-vaccination) and selected timepoints post-vaccination using an ELISA and/or SARS-CoV-2 immunoglobulin assay that is dependent on the SARS-CoV-2 N protein (e.g., N-ELISA or equivalent assay, such as the Roche Elecsys anti-SARS-CoV-2 assay), for participants that are N serology negative at baseline.

The proportion of participants who serologically converted will be graphically visualized and tabulated at every available timepoint by randomized group, together with the numbers of participants with an available measurement.

The number of participants with missing baseline N serology results will also be summarized.

Additional tabulation will summarize the number of participants with and without a SARS-CoV-2 infection as having:

Not infected

Asymptomatic or undetected participants

Antibodies binding to the SARS-CoV-2 nucleocapsid (N) protein

For antibodies binding to the SARS-CoV-2 nucleocapsid (N) protein, the number and percentage of participants with a positive sample at Day 1, Day 29, Day 71, Week 32 and Week 60 (if applicable) will be tabulated. A positive or negative result will be obtained from the assay (qualitative assay).

In contrast to the other immunogenicity analyses, this analysis will be performed only on the FAS.

The definition of the PPI analysis set incorporates the N-serology sample positivity assessment: immunogenicity samples obtained after a positive N-serology result post baseline will be excluded from the PPI analysis if the baseline N serology result was negative, as this is indicative of a SARS-CoV-2 infection during the study.

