1.2. Objectives and Endpoints for Participants in the Sub Study

Objectives	Endpoints
Secondary	
To assess the humoral immune response and durability to Ad26.COVID2.S across all groups in the sub study, at all blood collection timepoints.	
 Serological response to vaccination and binding antibody GMCs to SARS.COVID-2 S protein as measured by ELISA, or equivalent assay.
To assess the safety and reactogenicity of Ad26.COVID2.S administered at several dose levels	
 Solicited local and systemic AEs for 7 days after each vaccination Unsolicited AEs for 28 days after each vaccination SAEs throughout the study (from first vaccination until end of the study) Adverse events of special interest (AESIs [from first vaccination until end of the study]) MAAEs (until 6 months post-dose 2)

Exploratory	
To further explore humoral immune response to Ad26.COVID-19 across all groups in the sub study at all or selected blood collection timepoints.	
Exploratory analyses may include the following:
 
 • SARS-CoV-2 neutralization as assessed by SARS-CoV-2 neutralization assays VNA (wtVNA and/or psVNA) including neutralization of emerging SARS-CoV-2 variants • SARS-CoV-2 binding antibodies against emerging SARS-CoV-2 variants as assessed by S-ELISA or equivalent assay • Adenovirus neutralization • Functional and molecular antibody characterization including Fc-mediated viral clearance, avidity, Fc characteristics, immunoglobulin (Ig) subclass and IgG isotype • Analysis of circulating Spike protein • Epitope-specificity characterization of antibodies • Cytokine profiling: Analysis of cytokines, chemokines, and other proteins of the innate or adaptive immune response in the serum or plasma
To assess the correlation between the binding antibodies (ELISA) titers and neutralizing antibody (VNA) titers to SARS-CoV-2, in a subset of participants at selected timepoints.	Correlation between ELISA (S-ELISA; EU/mL) and VNA (wild-type virus [wt]VNA and/or pseudo virion [ps]VNA) titers at selected timepoints
To assess for the occurrence of asymptomatic SARS-CoV-2 infection.	The number of participants with positive non-S protein ELISA or equivalent assay (e.g., nucleocapsid [N] protein ELISA).

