Per amendment 5, an additional enrollment of adult participants 18 to 55 years, inclusive, will enroll into the sub study, into group 1, 3, 5 and 6 to further characterize the innate, pro-inflammatory and other relevant (e.g., pro-thrombotic) response to the Ad26.COV2.S to better understand a possible risk to TTS events. Participants will receive Ad26.COV2.S administered IM.

A target of approximately 240 participants (approximately 40 seronegative and approximately 20 seropositive participants per dose regimen) will be enrolled in the sub study and will receive a 2-dose vaccination regimen at either 9×10^{10} vp, 5×10^{10} vp, 2.5×10^{10} vp or 1.25×10^{10} vp.

Table 3 : Schematic Overview of Study Design and Groups for the Sub Study

Group	N seronegative	N seropositive	Day 1 Vaccination 1	Day 57 Vaccination 2
1	N ~ 40	N ~ 20	Ad26.COV2.S 9×10^{10} vp	Ad26.COV2.S 9×10^{10} vp
3	N ~ 40	N ~ 20	Ad26.COV2.S 5×10^{10} vp	Ad26.COV2.S 5×10^{10} vp
5	N ~ 40	N ~ 20	Ad26.COV2.S 2.5×10^{10} vp	Ad26.COV2.S 2.5×10^{10} vp
6	N ~ 40	N ~ 20	Ad26.COV2.S 1.25×10^{10} vp	Ad26.COV2.S 1.25×10^{10} vp

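### Values capped at the ULOQ make a 4-fold response unattainable once baseline exceeds ULOQ/4, so sero-response in participants with pre-existing S antibody can be understated

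*SAP*

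**What the plan says.** The core responder definition in SAP 6.1.4, used for S-ELISA and for both VNA formats, has two branches. A participant with baseline at or below the LLOQ responds by exceeding the LLOQ later. The other branch begins "The baseline (pre-dose 1) sample value is strictly greater than the LLOQ" and requires that "the post-baseline sample value represents an at least 4-fold" increase be seen. The alternative FDA-requested definition, which is exploratory, has the same 4-fold branch.

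SAP 6.1.2 states, separately for geometric means and for fold increases from baseline, that "Values > ULOQ are imputed with ULOQ". It adds one safeguard: if ">10% of data points in PPI or NI Set data values are > ULOQ", then "a selection of descriptive immunogenicity assessments will be repeated without a ULOQ". It does not list what belongs to that selection.

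The endpoint is secondary in the main study and in the sub study (SAP 1.2: "Serological response to vaccination and binding antibody GMCs"). The sub study plans "approximately 40 seronegative and approximately 20 seropositive participants per dose regimen". For analysis, baseline serostatus is set by central testing, and a positive result on S-ELISA, on a non-S assay, or on both counts as positive (SAP 5.1.5).

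**The concern.** A 4-fold criterion is a fold increase from baseline, and 6.1.2 gives the only ULOQ rule for one. If capped values feed the responder flag, a participant who starts high on the assay range has no room to show a 4-fold rise. A true 10-fold rise from ULOQ/3 would be recorded as a 3-fold rise, classed as non-response and kept in the denominator.

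The effect runs one way and falls on participants who already have S antibody at baseline. In the sub study, one third of planned participants are seropositive. Their response rate could then partly reflect the upper limit of the assay, and a reader of the table could not see how many non-responses were forced.

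**Working it through.** **Ceiling.** Let U be the ULOQ and b the baseline, with b > LLOQ. The largest capped fold is U / min(b, U).

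- b = 0.10 U gives 10.
- b = 0.20 U gives 5.
- b = 0.25 U gives exactly 4.
- b = 0.50 U gives 2.
- b ≥ U gives 1.

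The threshold ULOQ/4 is therefore exact. At b ≤ U/4 no true responder is lost: a true rise of at least 4-fold takes the value to at least 4b, and capping at U ≥ 4b leaves the ratio at 4 or more. A response is lost only if b > U/4 **and** the true rise is at least 4-fold, in which case the post-baseline value is above U. If b > U/4 and the post-baseline value is at or below U, the true ratio is below 4 and non-response is correct.

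**Size.** The documents give no ULOQ, no baseline distribution and no sero-response rate, so there is no stated figure to reproduce. The following are assumptions: among participants with baseline > LLOQ, log10 baseline is normal with SD 0.5, log10 true fold rise is normal with SD 0.5, the two are independent, and U = k × the baseline geometric mean.

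- Share that cannot respond: P = 1 − Φ(log10(k/4)/0.5).
- True response rate: R = Φ(log10(G/4)/0.5) for geometric mean rise G. This gives 0.787 for G = 10 and 0.500 for G = 4.
- True responders lost: R × P.
- Rate on capped values: R × (1 − P).

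| k | P (cannot respond) | Lost, G = 10 | Capped rate, G = 10 (true 78.7%) | Lost, G = 4 |
|---|---|---|---|---|
| 5 | 42.3% | 33% | 45% | 21% |
| 10 | 21.3% | 17% | 62% | 11% |
| 20 | 8.1% | 6% | 72% | 4% |
| 40 | 2.3% | 2% | 77% | 1% |
| 100 | 0.3% | 0.2% | 78% | 0.1% |

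P is an upper bound on the loss. With 20 seropositives per dose group, all with baseline above the LLOQ, P corresponds to about 8, 4, 2 and 0 people at k = 5, 10, 20 and 40.

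**Does the uncapped repeat catch it?** As written, the trigger counts data points over the whole PPI or NI set. The NI set excludes baseline seropositives, so it cannot reveal a ceiling in them. In the PPI set, take the four samples to Day 71 (three of them post-baseline) and count only seropositives' post-baseline values above the ULOQ:

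- Planned share 80/1,590 = 5.0%, all post-baseline values above the ULOQ: 5.0% × 3/4 = 3.8%. No trigger.
- Share 10%, roughly the level at which SAP 5.1.5 starts the serostatus subgroup analysis, all above: 10% × 3/4 = 7.5%. No trigger.
- Share 27%, half above: 27% × 0.5 × 3/4 = 10.1%. Trigger just met.

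The 27% is the Day 29 N-positive proportion in SAP 3 and 4.2. Treating all of those participants as baseline positive is an upper bound, since the SAP attributes the figure to infection during the study, insensitive local tests, or both. Seronegative participants' values above the ULOQ also count toward the pooled trigger. So the repeat may or may not start, and if it starts the SAP does not say that sero-response is included.

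**The case against.** Section 6.1.4 speaks only of the sample value and does not itself say that imputed values are used. The link to 6.1.2 is inferred, and 6.1.4 leaves further or updated rules to the Data Presentation Specifications, which are not among the documents. This stands as a limit on certainty. It does not remove the point, because 6.1.2 is the only ULOQ rule the SAP gives for a fold rise, and a secondary endpoint should be defined without ambiguity in the SAP.

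A reader might infer that sero-response in seropositives **is** understated, and that the 42%, 21%, 8% and 2% are misclassification rates. The documents support neither inference. Without the ULOQ and baseline levels, bias is possible but not shown, and those percentages exceed the loss because some of these participants have no true 4-fold rise. Nor are all seropositives exposed: those positive only by N serology, with S at or below the LLOQ, fall under the first branch.

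A reader might also infer that the repeat can never start. That holds only for seropositives alone at the planned 5.0% share; the 27% figure shows the share may be larger.

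The SAP also plans dot plots, participant profiles, reverse distribution curves and graphs showing the ULOQ in use. These should make a ceiling visible, but they do not correct the rate. Seroconversion in SAP 5.6.1 is confined to baseline seronegatives, response is descriptive, and no between-dose test of it is planned.

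**Conclusion.** The point holds in conditional form. On the natural reading of SAP 6.1.2 with 6.1.4, baseline above both LLOQ and ULOQ/4 makes response impossible on capped values, so sero-response in participants with pre-existing S antibody can be understated. The direction is certain if capped values are used. The size is not: in the tabulated scenarios it runs from about 33 percentage points to close to zero, and it rests on assumed SDs of 0.5, assumed mean rises of 4 or 10, and an assumed position of the ULOQ. Participants with baseline at or below the LLOQ are unaffected, as is the primary non-inferiority test, which uses log10 S-ELISA concentrations and not the responder flag. This is a minor point about a secondary endpoint, worth settling because the remedy is cheap.

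**What to change.** In SAP 6.1.4, state whether the 4-fold rule uses ULOQ-imputed values. Where it does, class a participant with baseline > LLOQ and > ULOQ/4 and a post-baseline value > ULOQ as undetermined, not as a non-responder. Report the number undetermined by dose and baseline serostatus, with the response rate under both bounds: all of them responders, and none of them.

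Do not drop them from the denominator. Everyone left with baseline > ULOQ/4 would then be a non-responder, so exclusion conditions on the outcome. With k = 5 and G = 10, exclusion removes 39% and gives 0.454/(1 − 0.386) = 74% against a true 79%. The bounds, 45% and 45% + 39% = 84%, contain the true rate.

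In SAP 6.1.2, name sero-response among the assessments repeated without a ULOQ, and assess the 10% trigger within baseline seropositives.

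The cost is a few sentences, a programming flag and one more descriptive table, and a range in place of a single rate where undetermined cases occur.

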6. STUDY VACCINATION AND CONCOMITANT THERAPY

6.1. Study Vaccines Administered

Ad26.COV2.S will be supplied at a concentration of 2×10^{11} vp/mL as a suspension in single-use vials, with an extractable volume of 0.5 mL. Formulation buffer of Ad26.COV2.S will be supplied as diluent containing 15 mM citrate, 5% (w/w) hydroxypropyl- β -cyclodextrin, 0.4% (w/w) ethanol, 0.03% (w/w) polysorbate 80, 75 mM NaCl, pH 6.2.

Participants will be vaccinated on Day 1 and Day 57.

A volume of 0.5 mL will be administered to all participants.

9 $\times 10^{10}$ vp dose level (Group 1):

- 0.5 mL is withdrawn from vial 1 containing 0.75 mL 2×10^{11} vp/mL and added to vial 2 containing 0.75 mL of 2×10^{11} vp/mL. 0.15 mL is withdrawn from a vial containing 1.2 mL formulation buffer and is added to vial 2 containing 1.25 mL 2×10^{11} vp/mL. The solution is mixed and 0.5 mL is withdrawn from vial 2 (Ad26.COV2.S vial) for dosing 9 $\times 10^{10}$ vp.

7x10¹⁰ vp dose level (Group 2):

- 0.3 mL is withdrawn from a vial containing 1.2 mL formulation buffer and added to a vial containing 0.75 mL 2x10¹¹ vp/mL. The solution is mixed and 0.5 mL is withdrawn from the Ad26.COV2.S vial for dosing 7x10¹⁰ vp.

5x10¹⁰ vp dose level (Group 3):

- 0.75 mL of formulation buffer is added to a vial containing 0.75 mL 2x10¹¹ vp/mL, providing 1x10¹¹ vp/mL in a vial with an extractable volume of more than 1 mL. Then 0.5 mL will be withdrawn from this vial for dosing 5x10¹⁰ vp.

3.5x10¹⁰ vp dose level (Group 4):

- 0.5 mL is withdrawn from vial 1 (Ad26.COV2.S vial) containing 0.75 mL 2x10¹¹ vp/mL and added to a vial containing 1.2 mL formulation buffer, leading to solution A. 0.15 mL is withdrawn from vial 2 (Ad26.COV2.S vial) containing 0.75 mL 2x10¹¹ vp/mL and added to solution A, leading to solution B. Solution B is mixed and 0.5mL withdrawn from solution B for dosing 3.5x10¹⁰ vp.

2.5x10¹⁰ vp dose level (Group 5):

- 0.4 mL is withdrawn from a vial containing 0.75 mL 2x10¹¹ vp/mL and added to a vial containing 1.2 mL formulation buffer. The solution is mixed and 0.5mL is withdrawn from the formulation buffer vial for dosing 2.5x10¹⁰ vp.

1.25x10¹⁰ vp dose level (Group 6):

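### The unadjusted Day 57 Ad26 to Day 71 S-antibody correlation could understate vector interference with dose 2; add a version adjusted for Day 57 S antibody (exploratory, low priority)

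*SAP*

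**What the plan says.** SAP section 6.1.4 gives the purpose as "to assess the impact of pre-existing Ad26 neutralizing antibodies in humoral immunogenicity against SARS-CoV-2". Ad26 VNA is measured in a subset at Day 1 and Day 57. The planned statistic is a "Spearman correlation between Ad26 VNA at Day 1 (if sufficient number of Ad26-seropositive participants) or Day 57 and S-ELISA concentrations", and the pairing of time points is fixed by the end of the same sentence: "wtVNA titers at Day 29 or Day 71, respectively, will be calculated and visualized with a scatterplot". So Day 1 Ad26 goes with Day 29, and Day 57 Ad26 goes with Day 71.

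The outcome is the level reached, not a rise. The text names concentrations and titres, and of the assay scatterplots it says "These scatterplots will display the values as analyzed for the geometric mean calculations". The section does plan a rise from the pre-dose-2 sample for S-ELISA and VNA ("fold increase from pre-dose 2 (for time points after dose 2) will be tabulated and graphically presented"), but only as a summary that is not linked to Ad26 titre. Nothing in sections 5.7 or 6.1.4 adjusts the Ad26 correlation for Day 57 S antibody.

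Protocol section 6.1 states the schedule: "Participants will be vaccinated on Day 1 and Day 57". Protocol section 2 describes the product as an Ad26 vector encoding S.

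**The concern.** The Day 1 Ad26 titre is a true pre-vaccination baseline. The Day 57 titre is not. It is taken 56 days after an Ad26-vector dose and can contain antibody raised by that dose, on top of any natural immunity. The same dose raises S antibody, and part of the Day 57 S level persists into Day 71. If people who respond strongly to dose 1 tend to be high on both markers, the Day 57 to Day 71 correlation gains a positive part that has nothing to do with interference, and this works against the negative part the analysis is meant to show. A coefficient near zero would then fit both no interference and real interference.

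The Day 1 pairing is free of this problem, but it is run only if enough participants are Ad26-seropositive before vaccination. If they are not, the Day 57 pairing is the only correlation left. What is at stake is the interpretation of an exploratory result about the two-dose schedule.

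**Working it through.** The plan gives no expected correlation, sample size or power for this analysis, so there is no figure of its own to reproduce. The check is an illustration within one dose level.

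**Inputs**
- SD of log10 S antibody = 0.5 (Protocol 9.2, SAP 3). The same SD is assumed for log10 Ad26 titre.
- Assumed, not in the documents: correlation ρ of Day 57 Ad26 (A) with Day 57 S (S57), 0 to 0.5; carry-over c = 0.7; interference slope g, 0 to −0.3 log10 per log10 Ad26; residual SD 0.3.

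**Model:** S71 = c × S57 + g × A + error.

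**Formulas**
- Covariance of A and S71 = 0.25 × (cρ + g).
- Variance of S71 = 0.25 × (c² + g² + 2cgρ) + 0.09.
- r = covariance / (0.5 × SD of S71); Spearman = (6/π) × arcsin(r/2).

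**Worked case, g = −0.2, ρ = 0.5:** covariance = 0.25 × (0.35 − 0.20) = 0.0375. Variance = 0.25 × (0.49 + 0.04 − 0.14) + 0.09 = 0.1875, SD 0.433. r = 0.0375 / 0.2165 = 0.173. Spearman = +0.166.

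The planned coefficient by this formula, with the partial Spearman given S57 by simulation:

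| ρ | planned, g = 0 | planned, g = −0.2 | partial, g = 0 | partial, g = −0.2 |
|---|---|---|---|---|
| 0 | 0.00 | −0.20 | 0.00 | −0.30 |
| 0.2 | +0.15 | −0.06 | 0.00 | −0.29 |
| 0.3 | +0.22 | +0.01 | +0.01 | −0.28 |
| 0.5 | +0.36 | +0.17 | +0.01 | −0.25 |

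Simulation of the planned coefficient agrees with the formula to within 0.01.

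**Where the sign turns.** The covariance is positive when ρ > |g|/c. For g = −0.2 that is 0.2/0.7 = 0.29. A smaller effect is masked sooner: at g = −0.1 the planned coefficient is already +0.04 at ρ = 0.2. A larger one holds out longer: at g = −0.3 it is −0.17, −0.10 and −0.02 at ρ = 0.2, 0.3 and 0.4, and about +0.06 at 0.5.

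**A second model** with full carry-over (c = 1) and residual SD 0.2 to 0.3 behaves the same way. At g = −0.2 the planned coefficient is −0.16 to −0.18 at ρ = 0, 0.00 at 0.2, +0.09 at 0.3 and +0.26 to +0.29 at 0.5.

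**Fold rise is not a safe substitute.** In the first model with no interference, correlating A with S71/S57 gives −0.09 at ρ = 0.2 and −0.21 at ρ = 0.5. This is a false signal, because a high S57 lowers the ratio.

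**How far the partial coefficient can be trusted.** In the table, responsiveness acts only through S57. Suppose instead that the same personal trait also raises the dose-2 response by 0.1 to 0.2 log10 per SD, with total residual SD kept at 0.3. For ρ from 0.2 to 0.5 and no interference, the partial Spearman is then +0.12 to +0.30 (planned: +0.22 to +0.55). With g = −0.2 it is −0.18 to −0.01 (planned: +0.03 to +0.41). It is nearer to zero when there is no effect and negative when there is one, but it is not clean.

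**The case against.** The case against is substantial.

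- **The purpose can be read more loosely.** The SAP speaks of impact on humoral immunogenicity and does not mention a dose-2 increment. Day 71 is the primary post-dose-2 time point, and relating Ad26 titre to the level reached there is a legitimate description. This stands, and is why the planned coefficient should be kept. It does not make that coefficient a measure of impact.
- **The premise is an inference.** The documents contain no data on Ad26 antibody induced by dose 1, and none on its correlation with S antibody. That dose 1 contributes to the Day 57 titre is a fair inference from the schedule and the product. That it contributes most of it is not established. At ρ = 0 the planned coefficient keeps the right sign.
- **Parts are covered or deferred.** SAP 6.1 has data analysed by vaccine group, which would remove differences between dose levels but not differences between people within a level. SAP 6.1.4 leaves further detail to the Data Presentation Specifications, which are not available here; the SAP does not say that they will add an adjustment.
- **The analysis is minor.** It is exploratory, optional, on a subset of unstated size, and has no test, threshold or decision rule. This stands and sets the priority.

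A reader might infer that the plan will report no association where interference exists, or that its coefficient has the wrong sign. The documents do not support that, because both quantities that decide it are unknown.

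**Conclusion.** The point holds as a possibility. The planned Day 57 to Day 71 coefficient could be shifted upward by a shared dose-1 component, and interference could then look weak, absent or reversed. With the assumed slope of −0.2 and carry-over of 0.7, the coefficient runs from −0.20 at a Day 57 correlation of 0 to +0.17 at 0.5, and changes sign near 0.29. These figures rest on an assumed correlation, slope, carry-over, residual SD and Ad26 SD; they show a range and do not predict the result.

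Nor should a reader infer that the two-dose non-inferiority conclusions are in doubt. Ad26 VNA enters neither the hypotheses (SAP 2), the analysis sets (SAP 4) nor the primary model (SAP 5.5.3.1). The Day 1 to Day 29 pairing is unaffected. This is an optional improvement of low priority.

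**What to change.** In SAP 6.1.4, for the Day 57 to Day 71 pairing only, add a partial Spearman correlation of Day 57 Ad26 VNA with the Day 71 value, adjusted for the Day 57 value of the same assay and calculated within dose level. Apply it to S-ELISA for everyone in the Ad26 subset with the needed samples, and to VNA only where Day 57 VNA was assayed. Report it beside the planned coefficient and scatterplot, and state that it reduces confounding by general responsiveness but may not remove it. Leave the Day 1 to Day 29 analysis as it is.

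The cost is a sentence or two of SAP text and a few lines of code. No new sample is needed for S-ELISA: serum is drawn before dose 2 from all participants (Protocol 1.4 and Table 3), and S-ELISA is planned on all participants' samples (Protocol 9.2.1) and at all blood collection time points (SAP 5.6).
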